### Exclusion Criteria:

- 1) Cancer surgery planned in the next 9 weeks
- 2) Treatment with radiation planned for the next 9 weeks
- 3) Actively trying to quit smoking, or planning to in the next 30 days. (If a subject reports that they plan to quit smoking in the next 30 days, we will call them after the 30 days to see if they are still trying to quit.)
- 4) Any use of e-cigarettes in the past 30 days
- 5) Pregnant or trying to get pregnant

## RECRUITMENT

Potentially eligible patients will be identified by clinician-researcher collaborators and through clinical trials nurses or clinical research coordinators, who monitor the cancer patient population for recruitment into clinical studies. Patients may be identified in multiple clinical settings, including outpatient clinics and the infusion suite. Once a potentially eligible patient is identified, a referral will be made to the site coordinator, who will meet with the patient, confirm eligibility, and obtain consent for the patient to participate in the study, and register the patient in the Velos e-Research database. (If a site coordinator is unable to utilize Velos, that coordinator will submit participant data to another coordinator with access and it will be entered into the Velos e-Research database.) The coordinator will conduct baseline web assessments, provide e-cigarettes and instruction on how to use the product, and conduct all follow up assessments.

## STUDY TIMELINE AND FOLLOW-UP

The trial is designed to allow for patient visits every 3 weeks for 12 weeks. The coordinators will work with the participant and the participants' medical care teams to schedule and conduct the visits. We will contact enrolled subjects for follow-up at 6 and 12 months after enrollment. Each time, we will attempt to contact the subjects 3 times by phone over a period of 3 weeks. During the call the subject will be asked if they are still using an e-cigarette, what brand they are using, what concentration of nicotine they use, how many times a day they use it, and how often they currently smoking any combustible tobacco products.

Participants will receive free e-cigarette products for the first 9 weeks of the trial and \$20 for each visit (\$100 total). Participants that travel more than 20 miles one-way for a study-only visit (no other appointments scheduled on the day of their study visit) will be given a \$10 gas card.

Time	Baseline	3 weeks	6 weeks	9 weeks	12 weeks
Activity	Consent; survey; ecig instruction; urine; CO	Survey; ecig refill; urine; CO	Survey; ecig refill; CO	Survey; qualitative interview; urine; CO	Survey; CO
Compensation	\$20	\$20	\$20	\$20	\$20

## OUTCOMES ASSESSMENT

Each visit will include a checklist that assesses how the participant is using the e-cigarettes and what problems he/she may be encountering with the use of the e-cigarette device. Adverse events will be assessed with a checklist for commonly occurring side effects from e-cigarettes and nicotine products. The coordinators will conduct and audio-record a 10-15 minute qualitative interview at 9 weeks soliciting perceptions about e-cigarettes to be transcribed and analyzed for common themes that could be useful in developing the larger intervention.

*Behavioral assessments:* We will use a Timeline Follow-Back Questionnaire (TLFB) to document use of cigarettes at baseline and cigarettes/e-cigarettes at baseline, 3, 6, 9, and 12 weeks. At follow up visits participants will be instructed to bring in all used and unused e- cigarettes, in order to verify reports of e-cigarette use. We will evaluate appeal with attitudinal ratings, on a 5-point Likert-type scale, e-cigarette ease of use, satisfaction, and enjoyment, and willingness to continue to purchase e-cigarettes in the future. All questionnaires are being programmed using a secure web-based system set up and maintained by the Dartmouth Bioinformatics group led by [name].

*Biomarkers of behavior:* Cigarette smoking will also be measured with exhaled carbon dioxide. We will assess expired breath CO2 using Micro Smokerlyzer meters (Bedfont Scientific), which have already been purchased for a previous study. The protocol will follow operating instructions that come with the devices, and the devices will be calibrated weekly with 40PPM CO2/air mixture. E-cigarette smoking will be measured with urine propylene glycol, the main constituent of e-cigarette aerosol. Some 40% of ingested

propylene glycol is excreted unchanged in the urine.

The NCCC Clinical Pharmacology Shared Resource (CPSR) will conduct assays of urine for smoke-related carcinogens. Urine samples (at least 20 mL) will be collected at the study defined time points from study participants in standard urine containers. These will be delivered to the NCCC CPSR, divided into 5 mL aliquots and stored at -20°C or below until analysis. Urine aliquots will be assayed in batches based on the published assays for urine nicotine, cotinine, 4- (methylnitrosamino)-1-(-3pyridyl)-1butanol (NNAL) and 1-hydroxy naphthalene (1-HOP) concentrations. These assays can and will be established and validated in the NCCC CPSR using the LC-MS/MS and HPLC-Fluorescence services available in the CPSR.

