## SPECIFIC AIMS AND HYPOTHESES

**Aim 1:** To evaluate the behavioral and psychological appeal of e-cigarettes among 40 chronic smokers with smoking-related cancers.

**Hypothesis 1 (H1):** Greater than 50% of study participants will report daily e-cigarette use at each assessment during the 9 weeks that e-cigs are provided, and mean satisfaction with e- cigarettes will be >4 on a 5-point scale. In a parallel process growth model for e-cigarette and cigarette use, there will be a significant negative correlation of growth slopes.

**Aim 2:** To evaluate the effect of e-cigarettes on biological markers of combusted tobacco toxicity.

**Hypothesis 2 (H2):** After 9 weeks, mean expired breath CO2 and urine NNAL will be reduced.

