HALO manufactures its e-cigarette and the nicotine solutions in the United States. The HALO solution e-cigarettes contain 0, 12, 18, 24, or 36 mg/ml nicotine. We have been advised to begin our participants with 18mg/ml and move up or down based on patient preference. E-cigarette liquid also comes in many flavors, and we have decided to allow participants to choose from four options. Halo has agreed to provide us with the names of their 4 highest selling liquids. They have shared an ingredients list with the Drs. [name] and [name] for the purposes of adverse event monitoring and in the event that our IRB members request information about the ingredients.

Figure 6. Starter kit for the Halo Triton tank.

Coordinators will assess participants at baseline and weeks 3, 6, 9, and 12. Although most of our patients are expected to have completed their therapy, the schedule is designed to integrate with return schedules for many chemotherapeutic regimens, if possible. We have considered the concern that chemotherapy could affect cigarette consumption or excretion of nicotine metabolites. According to our clinicians, the current chemotherapy regimens for these cancers are not associated with severe symptoms, such that patients rarely decrease their smoking during treatment. Nevertheless, we will assess the severity of 6 common chemotherapy side effects at each visit so that may be entered as a covariate in our analytic models. Regarding metabolites, for nicotine, the major metabolite cotinine is formed via CYP2A6 and CYP2B6 metabolism, and the traditional cytotoxic chemotherapeutic agents used in the cancer treatment are not known to affect the activity of these CYP450 /UGT enzymes significantly. Additionally, cyclical cytotoxic chemotherapy is not given every day throughout a cycle. The most well characterized carcinogens of smoking so far are NNK (4-(methylnitrosamino)1(3-pyridyl)-1-butanone) and NNAL (4-(methylnitrosamino)1(3-pyridyl)-1-butanol). These carcinogens are also metabolized by some of the same enzymes that metabolize nicotine including CYP2A6, UGT2B10, UGT1A4 and CYP2A13, so these should not be affected by most chemotherapeutic regimens.

Coordinators will assess eligibility, collect specimens, administer CO2 measurements and administer the surveys during the baseline and follow up visits.

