## PARTICIPANTS

### Inclusion Criteria:

- 1) Histological or cytological diagnosis of aerodigestive tract cancers or bladder cancer within the past 5 years (more than one tobacco-related malignancy is allowed)
- 2) AJCC stages I-IV
- 3) Daily smoking (at least 10 cigarettes per day for 10 years) and breath CO2 ≥8 ppm
- 4) Does not wish to quit smoking now (anyone wishing to quit smoking will be referred for smoking cessation counselling through the WRJ VAMC or DHMC program)
- 5) May be receiving anti-cancer agents
- 6) Age 18 or older
- 7) Fluent in English
- 8) Patient must be capable and willing to provide informed written consent for study participation
- 9) Able to participate in study visits

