**Toxicity Assessment:** Our measures of toxicity, urine NNAL, 1-HOP and CO2 will be compared between the baseline and 9-week assessments via paired t-test. For NNAL, assuming a standard deviation of change in this measure of 3.8 pmol/mg creatinine (as was seen in Joseph et al. 2008), with 40 participants, this test will have 80% power at the two-sided 0.05 significance level to detect a change from baseline of 1.7 pmol/mg creatinine. There is not enough information available on 1-HOP to perform a test of power, so analysis of this metabolite is considered exploratory. For expired CO, assuming a standard deviation of change in this measure of 17.0 ppm, with 40 participants, a paired t-test comparing baseline to 9-week will have 80% power at the two-sided 0.05 significance level to detect a change from baseline that is 7.7 ppm. Additionally, since CO2 will be measured several times throughout the treatment period, the trajectory of change over time in this measure will be modeled via linear mixed effects models including random intercept and slope terms to account for repeated observations within individual. With repeated measurements of CO, the power for the mixed model will be greater than that of the paired t-test of change from baseline to detect this change over time.

We will also evaluate toxicity by analyzing cotinine level to assure that the adverse effect of increased cotinine (resultant from increased e-cigarette usage without similar decrease in combustible cigarettes). To do this, we will compute the number of participants with an increase in cotinine over the course of the study and consider this an adverse event. With 40 participants, confidence intervals around this adverse event percentage will be at most 0.32 percentage points. The table below gives the probability of observing at least 1 participant with an increase in cotinine given different true percentage of participants with this adverse event. For example, if the population-wide true percentage of participants with cotinine increase is 0.5%, then the probability of observing at least 1 of the 40 study participants with an increase is 0.18.

True percentage of participants with increase cotinine	Probability of observing at least 1 adverse event (increase in cotinine)
0.5%	0.18
1%	0.33
2%	0.55
5%	0.87
10%	0.99

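### Any rise in urine cotinine counts as an adverse event, so under the plan's own no-change expectation about 20 of 40 participants would be flagged by chance; separately, the breath gas is named both CO2 and CO

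*Combined protocol and SAP*

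**What the plan says.** **Cotinine.** The Toxicity Assessment text in the statistical chapter will count the participants whose cotinine goes up during the study and treat each as an adverse event. It sets no minimum rise, does not name the samples compared and does not mention urine dilution. The sentence before gives the worry: more e-cigarette use that is not matched by a fall in cigarettes. The counting rule does not repeat that condition. A table then gives the probability of at least one event among 40 for true rates from 0.5% to 10%. The Primary outcomes section expects cotinine to stay the same, because smokers regulate their nicotine intake. The Study Timeline table schedules urine at baseline, week 3 and week 9.

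**Breath gas.** CO2 or carbon dioxide appears eight times in five places:
- Hypothesis 2: "After 9 weeks, mean expired breath CO 2 and urine NNAL will be reduced".
- Study Design, coordinator duties: "administer CO 2 measurements and administer the surveys".
- Inclusion Criterion 3: "Daily smoking (at least 10 cigarettes per day for 10 years) and breath CO 2 ≥8 ppm".
- Outcomes Assessment, three times, including "Cigarette smoking will also be measured with exhaled carbon dioxide" and "the devices will be calibrated weekly with 40PPM CO 2 /air mixture".
- Toxicity Assessment, twice: "Our measures of toxicity, urine NNAL, 1-HOP and CO 2 will be compared between the baseline and 9-week assessments via paired t-test" and "since CO 2 will be measured several times throughout the treatment period".

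Carbon monoxide or CO appears in the Abbreviations, the Abstract, the Primary outcomes, all five visits of the Study Timeline table and the power basis (SD of change 17.0 ppm, detectable change 7.7 ppm). The sentence after the last CO2 mention, about the same mixed model, reads "With repeated measurements of CO, the power for the mixed model will be greater".

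**The concern.** An expectation of no change describes the average. Individual values still move up or down with assay error, hydration and day-to-day differences in nicotine use. A rule that counts any upward movement, however small, therefore catches a large share of participants when nothing has happened. The table treats an increase as a rare event, so the table and the counting rule do not describe the same thing. At stake is a safety percentage, labelled as adverse events, that a reader could take for harm from the product.

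The breath-gas problem is one of naming. It still matters because the CO2 wording sits in operative text: who may enter, what gas calibrates the meter, what H2 predicts and what the paired test compares.

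**Working it through.** **1. The plan's own figures reproduce.**
- Probability of at least one event in 40 is 1 − (1 − p)^40. For p = 0.5%, 1%, 2%, 5% and 10% this gives 0.182, 0.331, 0.554, 0.871 and 0.985. The plan prints 0.18, 0.33, 0.55, 0.87 and 0.99.
- Widest exact 95% interval, at 20 of 40: 0.338 to 0.662, width 0.324, which matches the stated 0.32 read as a proportion. That width already covers a 50% rate, so the difficulty is what the count means, not its precision.
- Paired t-test for CO, n = 40, two-sided 0.05: noncentrality 7.7 / (17.0/√40) = 2.86, 39 degrees of freedom, power 0.798 against the stated 80%.

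**2. The counting rule when nothing changes.** Assume symmetric within-person variation and no ties. The result does not depend on how large that variation is.
- Week 9 against baseline: P(increase) = 0.5. The count is Binomial(40, 0.5), with mean 20 and central 95% range 14 to 26. The table's top rate gives 40 × 0.10 = 4, and 20/4 = 5.
- A rise at either week 3 or week 9, with the three values exchangeable within a person (assumption): the only escape is for baseline to be the highest of the three, so P = 1 − 1/3 = 2/3. Mean 26.7, range 21 to 32.

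**3. If mean cotinine actually fell.** Suppose a 20% fall and log-normal within-person variation (assumptions; the documents give no such figures). With s = √(2 ln(1 + CV²)), the expected week 9 count is 40 × [1 − Φ(−ln 0.8 / s)]. This is 8.5, 11.8 or 14.8 for a CV of 20%, 30% or 50%, still above the table's top expectation of 4.

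**4. Can the count show a true rise?** Assume normally distributed changes. Test the week 9 count against 50%, rejecting at 27 or more or 13 or fewer (two-sided p = 0.038), and compare it with a paired t-test of the mean change.

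| True rise (SD of change) | Expected count | Power, count | Power, mean change |
|---|---|---|---|
| 0.25 | 23.9 | 21% | 34% |
| 0.454 | 27.0 | 57% | 80% |
| 0.59 | 28.9 | 80% | 95% |

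**5. Breath gas.** The plan gives no SD or effect for CO2, so no power for CO2 can be computed. If every entry reads CO, the power stays at 0.798 and n at 40.

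**The case against.** **The count does respond to a real rise.** A reader might infer that it could never show one. Step 4 does not support that: it reaches 80% power at 0.59 SD of change. A rise of 0.25 SD is mostly missed by the mean change as well. What stands is lower efficiency and a high background count.

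**The comparison is less open than it looks.** A reader might infer that the plan gives no guide to which samples are compared. The same section sets baseline against week 9 for the other toxicity measures, and week 9 is the last urine sample. That is the natural reading, so 20 of 40 is the main figure and about 27 of 40 belongs to a less natural one.

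**The cigarette-use condition is partly there.** It appears in the preceding sentence, which is visibly incomplete. This is unclear drafting, but the rule as written still counts without it.

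**The safety consequence is limited.** This is a 40-person single-arm pilot. Adverse events are also collected by checklist at each visit, urine is assayed in batches, and no review or stopping trigger is tied to the count. This lowers the stakes but does not make the percentage interpretable.

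**CO is plainly intended.** A reader might infer that the trial would measure the wrong gas or that its power is invalid. The documents do not support either: the abbreviations, abstract, outcomes, visit table and power basis all say CO, and Outcomes Assessment also defers to the device operating instructions. No effect on enrolment or results is shown.

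**Conclusion.** The cotinine rule is wrong as written and should be changed. If there is no true change and within-person variation is symmetric, it labels about 20 of 40 participants (14 to 26) with an adverse event at week 9, five times the highest rate the plan's table considers. The count would be mostly measurement variation. It also leaves out the condition that motivates it. The table's arithmetic is right; the event definition is at fault.

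The breath-gas contradiction is real but secondary. It is a naming correction, with no change to sample size or power.

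**What to change.** Before results are seen:
1. State that cotinine is compared from baseline to week 9, corrected for creatinine.
2. Report the mean change with a 95% CI.
3. Count only rises above a pre-stated minimum that exceeds assay and within-person variation, and give the source of that figure. The documents contain no such figure, so none is suggested here.
4. Say whether more e-cigarette use without a similar fall in cigarettes is part of the count.
5. Match the rates in the probability table to the redefined event.
6. Reconcile the breath-gas wording in Hypothesis 2, the coordinator duties, Inclusion Criterion 3, Outcomes Assessment (including the calibration gas) and Toxicity Assessment with the CO outcome, visit table and power basis.

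The cost is wording and a small extra analysis, with no new visits or samples. The NNAL power basis is already per mg creatinine. If creatinine is not being assayed, it would have to be run on stored urine: 2 × 40 = 80 samples for baseline and week 9, or at most 3 × 40 = 120 for all three visits.

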## STATISTICAL ANALYSIS AND POWER CONSIDERATIONS

[figure not shown]
### Qualitative Analysis

A follow up interview will be conducted at week 9. The interview will be transcribed and a thematic analysis will be conducted to evaluate common issues encountered by smokers with cancer patients who use e-cigarettes. Thematic analysis consists of examination of text by identifying and grouping themes, followed by coding, classifying, and developing categories. Transcripts are uploaded into a qualitative analytic software program and analyzed using Atlas.ti, a qualitative coding program. Co-investigator [name] has experience using similar qualitative methods to interview health professionals. She will supervise the coders, staff at the Centers for Health and Aging at Dartmouth who have been trained to perform similar analyses in other studies.

*Substitution assessment:* The proportion of participants who report use of e-cigarettes during each follow-up visit during treatment will also be computed (along with a 95% confidence interval). This proportion is expected to be at least 0.5. With 40 participants, width of a 95% confidence interval around this proportion will be at most 0.32. The satisfaction with e- cigarettes (averaged across 3 treatment assessments) will be summarized among participants using descriptive statistics and the amount of e-cigarette product returned at each follow-up period will be summarized across the treatment period.

To explicitly test the substitution/replacement mechanism of e-cigarettes, we will perform an exploratory parallel process growth model fit within a structural equation modeling framework. In this model the trajectory over time of both frequency/quantity of cigarette use and frequency/quantity of e-cigarette use will be modeled assuming individual-level latent intercept and slope (i.e., latent growth curve model). A significant negative association between the latent slope of e-cigarettes and the latent slope of combustible cigarettes would be consistent with the replacement/substitution hypothesis. The model provides an explicit statistical test of the hypothesis that, as e-cigarette usage increases, combustible cigarette usage decreases. Power for this analysis is computed as that for an individual-level correlation coefficient assuming 40 participants. There will be at least 80% power to detect a correlation that is at least -0.4 between these two individual-level slopes. Figure 7 shows a diagram of the parallel process growth model.

n

**Toxicity Assessment:** Our measures of toxicity, urine NNAL, 1-HOP and CO2 will be compared between the baseline and 9-week assessments via paired t-test. For NNAL, assuming a standard deviation of change in this measure of 3.8 pmol/mg creatinine (as was seen in Joseph et al. 2008), with 40 participants, this test will have 80% power at the two-sided 0.05 significance level to detect a change from baseline of 1.7 pmol/mg creatinine. There is not enough information available on 1-HOP to perform a test of power, so analysis of this metabolite is considered exploratory. For expired CO, assuming a standard deviation of change in this measure of 17.0 ppm, with 40 participants, a paired t-test comparing baseline to 9-week will have 80% power at the two-sided 0.05 significance level to detect a change from baseline that is 7.7 ppm. Additionally, since CO2 will be measured several times throughout the treatment period, the trajectory of change over time in this measure will be modeled via linear mixed effects models including random intercept and slope terms to account for repeated observations within individual. With repeated measurements of CO, the power for the mixed model will be greater than that of the paired t-test of change from baseline to detect this change over time.

We will also evaluate toxicity by analyzing cotinine level to assure that the adverse effect of increased cotinine (resultant from increased e-cigarette usage without similar decrease in combustible cigarettes). To do this, we will compute the number of participants with an increase in cotinine over the course of the study and consider this an adverse event. With 40 participants, confidence intervals around this adverse event percentage will be at most 0.32 percentage points. The table below gives the probability of observing at least 1 participant with an increase in cotinine given different true percentage of participants with this adverse event. For example, if the population-wide true percentage of participants with cotinine increase is 0.5%, then the probability of observing at least 1 of the 40 study participants with an increase is 0.18.

True percentage of participants with increase cotinine	Probability of observing at least 1 adverse event (increase in cotinine)
0.5%	0.18
1%	0.33
2%	0.55
5%	0.87
10%	0.99

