### Primary outcomes:

**Appeal (H1)**—E-cigarette use and amount of e-cigarette product used per week, proportion of participants that report e-cigarette use at each assessment, satisfaction scores for e-cigarettes, and whether they continue e-cigarette use at 12 weeks (3w after end of trial). Correlation between change in e-cigarette use and change in cigarette use.

Combustible Tobacco Toxicity (H2)—Exhaled CO, urine NNAL and 1-hydroxy naphthaline (1- HOP). Because smokers are good at regulating nicotine intake, we expect no change in urine cotinine over time.

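### Hypothesis 1 is about daily e-cigarette use in more than 50% of participants, but the primary outcome and the planned analysis count use with no frequency attached

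*Combined protocol and SAP*

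**What the plan says.** Specific Aims and Hypotheses, Hypothesis 1: "Greater than 50% of study participants will report daily e-cigarette use at each assessment during the 9 weeks that e-cigs are provided". Hypothesis 1 also has a satisfaction component and a growth-slope component, which are not at issue here.

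Primary outcomes, under Appeal (H1), lists the "proportion of participants that report e-cigarette use at each assessment". The word daily is absent. The same entry lists e-cigarette use and product used per week, satisfaction, continued use at week 12, and a correlation of changes.

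Statistical Analysis, Substitution assessment (printed under the Qualitative Analysis heading): "The proportion of participants who report use of e-cigarettes during each follow-up visit during treatment will also be computed", with a 95% confidence interval. It continues: "This proportion is expected to be at least 0.5". On precision: "With 40 participants, width of a 95% confidence interval around this proportion will be at most 0.32".

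The only planned analysis that mentions how often e-cigarettes are used is the growth model. It is labelled exploratory ("we will perform an exploratory parallel process growth model"), and in it "frequency/quantity of e-cigarette use will be modeled assuming individual-level latent intercept and slope".

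**The concern.** The 50% mark is carried from the hypothesis into the analysis, but the condition that gives it meaning is not. A participant who used the supplied product once or twice since the last visit could count as a user, with no stated look-back window, and so count towards a benchmark written for daily use.

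The Abstract makes the degree of adoption over the 9 supply weeks the overarching aim, and the pilot is meant to show whether a larger trial is feasible. If use is mostly occasional, the planned proportion could sit comfortably above one half while the hypothesis as written is false. The amount of product used and the growth model might hint at this. Neither yields a share of participants that can be compared with 50%.

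**Working it through.** **1. The passages side by side**

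| Place | Quantity | Frequency | Mark |
|---|---|---|---|
| Hypothesis 1 | share of participants, each assessment in the 9 weeks | daily | greater than 50% |
| Primary outcomes, Appeal (H1) | share of participants, each assessment | none | none |
| Substitution assessment | share of participants, each on-treatment follow-up visit | none | at least 0.5 |

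Elsewhere the protocol marks the distinction. Inclusion criterion 3 reads "Daily smoking (at least 10 cigarettes per day for 10 years", that is, daily with a stated minimum. Exclusion criterion 4 refers to any e-cigarette use and gives a 30-day window. Times of use per day is listed for the 6- and 12-month telephone calls, which come after supply ends.

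**2. The plan's own figure**

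The widest 95% interval with n = 40 occurs at 20/40.

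- Exact (Clopper-Pearson): 0.338 to 0.662, width 0.324, which rounds to the stated 0.32.
- Wald: 2 × 1.96 × √(0.5 × 0.5/40) = 0.310.
- Wilson: 0.296.

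The precision figure reproduces. The problem is one of definition, not arithmetic.

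**3. Direction**

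Let A be the number of users and D the number of daily users among 40. Every daily user is a user, so D ≤ A. The planned proportion A/40 is never below D/40.

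**4. Size (all rates assumed; the documents give none)**

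Count example with exact 95% intervals:

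- 28/40 users = 0.70 (0.535 to 0.834), above the mark.
- If 18 of them are daily users, 18/40 = 0.45 (0.293 to 0.615), not above it.
- If 25 of them are daily users, 25/40 = 0.625 (0.458 to 0.773), above it, so the reading does not change.

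More than 50% of 40 means at least 21. The share of users who must be daily users to reach 21 is 21/A: 88% of 24 users, 75% of 28, 66% of 32, 58% of 36.

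For probabilities, take A ~ Bin(40, a) and D ~ Bin(40, a·s), where a is the any-use rate and s the share of users who are daily users. Because D ≥ 21 implies A ≥ 21,

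P(A ≥ 21 and D ≤ 20) = P(A ≥ 21) − P(D ≥ 21).

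| a | s | a·s | P(A ≥ 21) | P(D ≥ 21) | Difference |
|---|---|---|---|---|---|
| 0.70 | 0.5 | 0.35 | 0.994 | 0.017 | 0.976 |
| 0.70 | 0.7 | 0.49 | 0.994 | 0.388 | 0.606 |
| 0.70 | 0.8 | 0.56 | 0.994 | 0.729 | 0.265 |
| 0.70 | 0.9 | 0.63 | 0.994 | 0.936 | 0.057 |
| 0.80 | 0.5 | 0.40 | >0.999 | 0.074 | 0.926 |
| 0.80 | 0.7 | 0.56 | >0.999 | 0.729 | 0.271 |
| 0.80 | 0.8 | 0.64 | >0.999 | 0.952 | 0.048 |
| 0.80 | 0.9 | 0.72 | >0.999 | 0.997 | 0.003 |

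These are single-visit figures. Hypothesis 1 asks for more than 50% at every assessment. If weeks 3, 6 and 9 were independent, which they will not be, the case a = 0.70, s = 0.8 would give 0.994³ − 0.729³ ≈ 0.98 − 0.39 ≈ 0.59 in place of 0.27.

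**5. The two wordings of the mark**

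At least 0.5 and greater than 50% differ only at exactly 20 of 40, which has probability 0.125 if the true rate is 0.5 and 0.055 if it is 0.4 or 0.6. This is minor.

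**The case against.** The strongest reply is that neither the outcome nor the analysis says any use. Both say use, the outcome is labelled as belonging to Hypothesis 1, and the analysis repeats its 50% mark for the same period. Use may therefore be shorthand for the daily use already named, especially as the authors write any where they mean any. That reading is possible. But the word is missing in two separate places, and daily e-cigarette use is defined nowhere. Even on this reading the analyst has no rule for who counts, and the text as it stands permits the broader count.

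Second, extent of use is measured beyond yes or no: Timeline Follow-Back, a checklist at each visit, returned product and weekly amount. That is so, but no planned summary turns these into a share of daily users.

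Third, this is a 40-person single-arm pilot with a descriptive proportion, an expectation and no pass rule. This limits the consequence, and the 21-of-40 cut used above is only a reading of more than 50%. It does not excuse estimating something other than the hypothesised quantity.

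Fourth, the documents do not say that the Timeline Follow-Back records e-cigarette use day by day. This stands, and the cost of the fix depends on it.

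Finally, a figure at the head of the statistical section is not reproduced in the text available. The Primary outcomes section omits daily independently of it.

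**Conclusion.** The concern holds and should be fixed. The planned proportion does not carry the daily condition of Hypothesis 1, and no other planned summary supplies it. The discrepancy can run only one way, towards apparent support for the hypothesis. Its size depends on the share of users who are daily users, which the documents do not give: under the assumed rates, the chance of a misleading reading at one visit runs from about 0.98 down to 0.003. If nearly all users are daily users, the conclusion does not change, but the plan as written would not show which situation applies. The word may simply have been dropped. The satisfaction and slope components of Hypothesis 1 and the stated interval width are unaffected.

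**What to change.** Reconcile Hypothesis 1, the Primary outcomes section and the Substitution assessment.

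- In the last two, add the proportion of participants reporting daily e-cigarette use at each of weeks 3, 6 and 9, with its 95% confidence interval, as the quantity compared with the 50% mark.
- Before data are seen, define daily and its look-back window, and derive the measure from the Timeline Follow-Back already scheduled at those visits. Confirm that it is recorded by day for e-cigarettes.
- Keep any use as a separate descriptive line.
- State the denominator and the interval method, and write greater than 50% in both places.

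The cost is two or three sentences, with no added visits or participants. If daily records are not planned, the form needs a small change. The 0.32 width still holds, because it is a maximum for any proportion with 40 participants. The price is a stricter benchmark: with 70% any use and 80% of users daily (assumed), the chance of an observed proportion above 50% at a visit falls from 0.99 to 0.73. The result remains descriptive.
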